1.7 Subject's Duration of Participation

Approximately 33 male and female subjects 12 to 75 years of age will be enrolled in the study. Following the subject's first dosing with study drug, their participation in the study will be approximately 2 months, unless the subject is withdrawn early as specified in Section 9.3.2 or has a new or ongoing AE at the final safety assessment visit.

Subjects with ongoing AEs will be followed until the AE has resolved or stabilized (see Section 7.8.2). The estimated duration of the study from first subject in (FSI) to last subject out (LSO) is approximately 3 months.

2. STUDY OBJECTIVES

Primary Objective

- To evaluate the safety and tolerability of multiple C16G2 Varnish administrations in adolescent and adult dental subjects

Secondary Objectives

- To assess the targeted antimicrobial activity of C16G2 Varnish applications as measured by a reduction in *Streptococcus mutans* in saliva and dental plaque
- To assess total bacteria in saliva and dental plaque post-study drug administration

3. STUDY DESIGN

A single-blind, randomized, placebo-controlled Phase 2 study to evaluate the safety and oral microbiology of C16G2 Varnish application in male and female dental subjects 12-75 years of age. This multi-center study will evaluate multiple study drug administrations of C16G2 Varnish or Placebo.

Before dosing of study drug, eligible subjects will undergo professional dental prophylaxis 2-7 days prior to the first study drug administration. Subjects will receive five study drug applications over a 1-week period. Study drug will be applied with a small brush typically used in dental varnish administration. To evaluate the durability of *S. mutans* suppression, study subjects will be followed for microbiology for 1 month after the last study drug administration.

Clinic visits include Visit 1 (Screening/Days -30 to -1), Visit 2 (Prophylaxis/Day -7 to -2), Visits 3-5 (Confirmation of Eligibility, Baseline & Study Drug Administration), Follow-up Visits 6-8 (Safety and Microbiology) and Follow-up Visits 9-10 (Microbiology only).

Enrolled subjects will be assessed for safety and microbiology parameters. For details on study schedules including dosing and microbiology information refer to Appendix A. Details on study assessments & procedures are provided in Appendix B. For microbiology assessments refer to Appendix C.

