Exclusion Criteria:	Subjects are excluded from participation if any of the following apply:

	
 1. Advanced periodontal disease 2. Active caries lesion(s) within 30 days prior to study drug administration (confirmed by comprehensive caries examination including standard radiographs). Subjects presenting with insipient, non-cavitated lesion(s) are not excluded. Note: If radiographs are deemed appropriate for the study and taken within 6 months prior to the Screening visit, these may be used for determining eligibility and not required to be repeated at Screening 3. Partially erupted teeth where the entire crown is not erupted or an operculum is present 4. Medical condition (e.g., artificial heart valve, history of infective endocarditis, cardiac transplant with valvular dysfunction, congenital heart disease or total joint replacement) for which antibiotics are recommended prior to dental visits and/or procedures 5. Pathologic lesions of the oral cavity (suspicious or confirmed) 6. Full dentures or permanent orthodontic appliances, e.g., braces, lingual or buccal brackets Note: Partial dentures, removable retainers and night guards are not excluded, provided that they are cleaned regularly throughout the duration of the study 7. Use of systemic antibiotics, topical oral antibiotics, or use of other drugs, which in the opinion of the Investigator could influence the study outcome, beginning 30 days prior to Screening until the end of study participation 8. Medical history indicating the woman is pregnant, breastfeeding/lactating or has a positive urine pregnancy test 9. Participation in a clinical trial or receipt of a non-FDA approved therapy within 30 days prior to study drug administration (depending on the specifics, participation in an observational study is not necessarily excluded) 10. Presence of any condition or concurrent illness, which in the opinion of the Investigator, would compromise normal immune function (e.g., diabetes, rheumatoid arthritis, lupus, liver disease, organ transplant, etc.), interfere with the use of study dentifrice and oral care products, or interfere with the ability to comply with study requirements, or jeopardize the safety of the subject or the validity of the study results

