	
Instructions for the preparation of C16G2 Varnish or Placebo are provided in the Study Manual. Instructions for the application of study drug are provided in Appendix G.
 
 ○ Subjects will receive a single study drug application. Subjects will have C16G2 Varnish or Placebo applied to all tooth surfaces. Note: C16G2 Varnish or Placebo will not be actively removed, but remain on the subject's teeth until removed through normal wear and mastication after discharge 
Post-Dose
 
 ○ Photographic imaging immediately after study drug application (see instructions in Appendix H). ○ Oral Cavity Assessment (hard and soft tissues) ○ Vital Signs (blood pressure, heart rate, temperature) taken 1 hour \pm 15 minutes post study drug application ○ Subjects will not eat, swish, or drink anything besides plain water for one hour after study drug application. In addition, subjects will be advised to relax their jaws and to not grind their teeth. Subjects will be supervised to ensure compliance. ○ Adverse Events ○ Discharge 
Clinic Visit 6-8 (24 hours, 3 days and 7 days Post Visit 5)
 
Subjects will be scheduled for this visit between 6AM and 10AM
 
 ○ Concomitant Medication Update ○ Oral Cavity Assessment (Visits 6 & 8 ONLY) ○ Targeted Physical Exam (Visits 6 & 8 ONLY) ○ Microbiology (stimulated saliva and dental plaque collection) ○ Adverse Events ○ Discharge 
Clinic Visits 9 & 10 (Week 2 & 4 Post Visit 5)
 
Subjects will be scheduled for this visit between 6AM and 10AM.
 
 ○ Microbiology (stimulated saliva and dental plaque collection) ○ End of Study (Visit 10 only)
Subject Instructions:	
Enrolled subjects will be instructed to abstain from eating food and drinking beverages that contain a high sugar content (e.g., candy, soda with refined sugar, sugary snacks, dried fruit, fruit rolls) on the days of study drug administration (Visits 3-5). While smokers are not excluded from study participation, subjects should abstain from using chewing tobacco throughout the study.
 
a) Oral Hygiene Instructions
 
During the entire study subjects will not be allowed to use any dental material besides the material provided by the study center. Prior to attending the study center for any visit (Visits 1-10), subjects will not be allowed to perform

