4.2 Exclusion Criteria

Subjects are excluded from participation if any of the following apply:

1. Advanced periodontal disease
2. Active caries lesion(s) within 30 days prior to study drug administration (confirmed by comprehensive caries examination including standard radiographs). Subjects presenting with insipient, non-cavitated lesion(s) are not excluded.
Note: If radiographs are deemed appropriate for the study and taken within 6 months prior to the Screening visit, these may be used for determining eligibility and not required to be repeated at Screening
3. Partially erupted teeth where the entire crown is not erupted or an operculum is present
4. Medical condition (e.g., artificial heart valve, history of infective endocarditis, cardiac transplant with valvular dysfunction, congenital heart disease or total joint replacement) for which antibiotics are recommended prior to dental visits and/or procedures
5. Pathologic lesions of the oral cavity (suspicious or confirmed)
6. Full dentures or permanent orthodontic appliances, e.g., braces, buccal or lingual brackets.
Note: Partial dentures, removable retainers and night guards are not excluded, provided that they are cleaned regularly throughout the duration of the study
7. Use of systemic antibiotics, topical oral antibiotics, or use of other drugs, which in the opinion of the Investigator could influence the study outcome, beginning 30 days prior to Screening until the end of study participation
8. Medical history indicating the woman is pregnant, breastfeeding/lactating or has a positive urine pregnancy test
9. Participation in a clinical trial or receipt of a non-FDA approved therapy within 30 days prior to study drug administration (depending on the specifics, participation in an observational study is not necessarily excluded)
10. Presence of any condition or concurrent illness, which in the opinion of the Investigator, would compromise normal immune function (e.g., diabetes, rheumatoid arthritis, lupus, liver disease, organ transplant, etc.), interfere with the use of study dentifrice and oral care products, or interfere with the ability to comply with study requirements, or jeopardize the safety of the subject or the validity of the study results

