Subjects will be scheduled for these visits between 6AM and 10AM. Subjects should not be exposed to study drug if they present with any disruption or loss of integrity in the oral cavity mucosa, gingiva or have lip lesions, (e.g. aphthous stomatitis, active herpetic sores, cheek bites, or severely chapped or cracked lips, etc.).

Pre-Dose

- Concomitant Medications Update
- Vital Signs (blood pressure, heart rate, temperature) taken in supine or sitting position
- Microbiology (stimulated saliva and dental plaque collection)
- Oral Cavity Assessment (hard and soft tissues)
- Targeted Physical Exam (general, extraoral, head & neck) (Visit 4 ONLY)
- Oral Hygiene (including brushing and flossing will be conducted at the clinic prior to study drug administration)

Study Drug Administration:

Instructions for the preparation of C16G2 Varnish or Placebo are provided in the Study Manual. Instructions for the application of study drug are provided in Appendix G.

- Subjects will receive a single study drug application. Subjects will have C16G2 Varnish or Placebo applied to all tooth surfaces.

Note: C16G2 Varnish or Placebo will not be actively removed, but remain on the subject's teeth until removed through normal wear and mastication after discharge

Post-Dose

- Photographic imaging immediately after study drug application (see instructions in Appendix H).
- Oral Cavity Assessment (hard and soft tissues)
- Vital Signs (blood pressure, heart rate, temperature) taken in supine or sitting position 1 hour (\pm 15 minutes) post study drug application
- Subjects will not eat, swish, or drink anything besides plain water for one hour after study drug application. In addition, subjects will be advised to relax their jaws and to not grind their teeth. Subjects will be supervised to ensure compliance.
- Adverse Events
- Discharge

6.3.6.5 Clinic Visits 6-8 (24 hours, 3 days and 7 days Post Visit 5)

Subjects will be scheduled for this visit between 6AM and 10AM

- Concomitant Medication Update
- Oral Cavity Assessment (Visit 6 and 8 ONLY)
- Targeted Physical Exam (Visit 6 and 8 ONLY)
- Microbiology (stimulated saliva and dental plaque collection)
- Adverse Events
- Discharge

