6.3.6.6 Clinic Visits 9 & 10 (Week 2 & 4 Post Visit 5)

Subjects will be scheduled for this visit between 6AM and 10AM.

- Microbiology (stimulated saliva and dental plaque collection)
- End of Study (Visit 10 only)

Study Visit Schedule

STUDY PERIODS	VISIT #	SCHEDULE	TIME
Screening	1	Day -30 to -1	Morning (6-10 AM)
Prophylaxis	2	Day -7 to -2	Morning (6-10 AM)
Study Drug Administration	3 4 5	Day 0 24-48 hrs Post Visit 3 24-48 hrs Post Visit 4	Morning (6-10 AM)
Safety and Microbiology Follow-up	6 7 8	24 hours Post Visit 5 3 days Post Visit 5 7 Days ± 1 Day Post Visit 5	Morning (6-10 AM)
Microbiology Follow-up	9 10	14 Days ± 2 days Post Visit 5 28 Days ± 3 days Post Visit 5	Morning (6-10 AM)

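### Drugs that could alter the microbiology are barred to the end of participation, but no medication check is scheduled after Visit 8, so the late durability samples go unchecked

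*Combined protocol and SAP*

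**What the plan says.** Exclusion 7 (Synopsis and Section 4.2) covers "Use of systemic antibiotics, topical oral antibiotics, or use of other drugs, which in the opinion of the Investigator could influence the study outcome". The same sentence sets how long the bar lasts: "could influence the study outcome, beginning 30 days prior to Screening until the end of study participation".

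Section 3 divides the follow-up into "Follow-up Visits 6-8 (Safety and Microbiology) and Follow-up Visits 9-10 (Microbiology only". The list for Visits 6-8 (Synopsis; Section 6.3.6.5) contains a "Concomitant Medication Update". The next block, "Clinic Visits 9 & 10 (Week 2 & 4 Post Visit 5", has two entries: saliva and plaque sampling, and "End of Study (Visit 10 only". Appendix B agrees. Its concomitant-medication row is marked for Visits 1, 3, 4-5 and 6-8 and is blank for Visits 9-10. The Synopsis (Safety Monitoring) runs the general health question through Visit 8, and note k of Appendix B ends the adverse-event reminder there.

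The Synopsis and Section 3 say why sampling goes on to one month: to learn how long *S. mutans* suppression lasts. Section 9.3.2 lists a medication that could affect the outcome, with an antibiotic as its example, among the grounds on which a subject may be removed. Section 8.5 defines the microbiology sets without reference to such use. Section 8.7.6.5 gives no rule for affected samples and leaves further detail to a SAP.

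**The concern.** The bar on interfering drugs outlasts the procedure that would show whether it was kept, and the uncovered interval is the one that holds the durability samples.

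Suppose an active-arm subject takes an antibiotic between Visits 8 and 10 and nobody asks. A low *S. mutans* count at Visit 10 could then be read as lasting suppression by the varnish. In a placebo subject the same event would narrow the contrast with active. The medication summary in Section 8.7.2 could not separate no use from use that was never asked about. The removal ground in Section 9.3.2 and the deviation listing in Section 8.7.4 both need the use to be known first.

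**Working it through.** **1. Length of the unchecked interval.** The inputs come from the Study Visit Schedule in Section 6.3.6.6, repeated in Appendix D. Visit 8 is at "7 Days ± 1 Day Post Visit 5", that is days 6 to 8. Visits 9 and 10 are at "14 Days ± 2 days Post Visit 5 28 Days ± 3 days Post Visit 5", that is days 12 to 16 and days 25 to 31.

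- Visit 8 to Visit 10, nominal: 28 − 7 = 21 days.
- Shortest: 25 − 8 = 17 days. Longest: 31 − 6 = 25 days.
- Share of the time from Visit 5 to Visit 10: 21/28 = 75%; 17/25 = 68%; 25/31 = 81%.

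**2. Samples involved.** Sampling after the last dose takes place at Visits 6, 7, 8, 9 and 10, so 2 of 5 visits have no medication check. Two visits × two sample types = 4 samples per subject. That gives 11 × 4 = 44 in the first cohort and 33 × 4 = 132 if all three cohorts are filled. These are samples that go unchecked, not samples known to be affected.

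**3. Weight of one subject.** With full cohorts, one subject carries 1/8 = 12.5% of an active group's mean. In placebo the weight is 1/3 = 33% if reported per cohort, or 1/9 = 11% if pooled over three cohorts; the documents do not say which. Any outlier in a trial this small would carry the same weight.

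**4. Chance of at least one user.** The documents give no rate of barred-drug use. Assume, for illustration only, that a proportion *p* of subjects between 1% and 10% use a barred drug in the interval. The chance of at least one user among *n* is 1 − (1 − *p*)^*n*:

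| *n* | *p* = 1% | *p* = 10% |
|---|---|---|
| 8 (active group) | 8% | 57% |
| 3 (placebo, one cohort) | 3% | 27% |
| 33 (all subjects) | 28% | 97% |

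This is a chance of occurrence, not a bias. The documents also give no effect of such drugs on *S. mutans* counts.

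**5. Other routes by which use could become known.**

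- *Adverse events.* Section 7.1 records all events until discharge and, in its example, notes the treatment given. This conflicts with the Visit 8 stop in the Synopsis and in note k of Appendix B. It would also miss use that is not tied to a reported event.
- *Volunteered reports and unscheduled calls* (Synopsis, Safety Monitoring). Possible, but not planned contacts.
- *Source review.* Sections 9.2.2 and 9.3.1 give monitors access to medical and dental records, which helps only if the use is recorded there.
- *Withdrawal and exit evaluations.* Sections 9.3.2 and 9.3.3 include a medication update, but only for subjects still within the safety period. The Synopsis and Section 1.4 set that period at one week after dosing, so these evaluations do not cover the interval after Visit 8.

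**6. The cohort decision.** Section 8.2 places the microbiology review after Visit 8. The Synopsis (Treatment / Randomization) and Sections 3.1.1 and 8.6 describe a rolling review instead. On those passages, Visit 9-10 results could feed the decision to open further cohorts.

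**The case against.** The strongest reply is that the plan is not blind after Visit 8. An antibiotic is usually taken for an illness. Under Section 7.1 that illness would be a recordable event, with its treatment noted, up to discharge. Monitors can read the source records. The Visit 9-10 samples are also stored for qRT-PCR and community analysis (Appendix C), and a broad fall in bacteria there might prompt a query. The trial is descriptive and its primary objective is safety. Durability is a stated design purpose but not a listed objective. The Study Manual, the case report forms and any separate SAP are not among the documents and might contain a check.

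Much of this stands and sets the limits of the point. A reader might infer that affected late samples could never be identified. The documents do not support that, because the routes above could reveal some use. A reader might also infer that the durability results will be biased in favour of the drug. That is not supported either: no rate or effect is given, and the direction depends on which group the user is in. Nor do the visit schedules contradict one another; they consistently treat Visits 9 and 10 as sampling visits.

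What the reply does not supply is a planned question. Each route depends on an event being reported, a record being made or a stored sample being tested. A rule in a later SAP could not use data that were never collected.

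**Conclusion.** The point holds as a limited design gap that is cheap to close. If the protocol is followed exactly, the only samples beyond about one week after the last dose have no planned check for barred drugs over 21 days (17 to 25), although the bar itself runs to the end of participation. Use may still come to light, but not reliably.

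The safety analysis and the samples through Visit 8 are unaffected. For the durability reading, neither size nor direction of bias can be stated. It cannot be assumed that the cohort decision is insulated from the late samples, because the passages on when microbiology is reviewed differ.

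The conclusion assumes that the schedules in the protocol govern and that no medication question for Visits 9 and 10 sits in documents not supplied.

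**What to change.** 1. Add a medication update at Visits 9 and 10 in the Synopsis, Section 6.3.6.6 and Appendix B. All five post-treatment sampling visits would then have a check, and the unchecked stretch falls from 21 days to 0 for subjects who attend.
2. Add the same update to the withdrawal evaluations in Section 9.3.2 for subjects who leave after Visit 8, and to the matching list in Section 9.3.3.
3. Add a sensitivity summary to Section 8.7.6.5: *S. mutans* results with and without samples collected after a systemic or topical oral antibiotic that was started between Visit 3 and that sample. The summary of all samples stays the main one.
4. For other drugs under Exclusion 7, have the classification made without sight of the microbiology results and, where possible, of treatment assignment. Section 3.1.2 leaves the Investigator and the Sponsor's assigned team unblinded, so the rule needs this safeguard.
5. Reconcile the adverse-event recording period in Section 7.1 with the Visit 8 stop in the Synopsis and Appendix B, and the timing of the microbiology review in Section 8.2 with the Synopsis and Sections 3.1.1 and 8.6.

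The cost is one question and one form at two visits that already take place, and one extra summary. That summary will rest on few subjects: with three placebo subjects per cohort, one flagged subject leaves two.

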3.1 Blinding and Randomization

3.1.1 Randomization

The study will enroll subjects into up to three study arms. Up to 33 subjects will receive multiple doses of study drug (27.2 mg and/or 13.6 mg and/or 54.4 mg C16G2 Varnish or Placebo) applied with a small brush typically used in dental varnish administration (for details see Appendix A). Subjects will be enrolled in an 8:3 ratio. The Sponsor will perform unblinded microbiology review on an ongoing basis to determine whether to enroll additional 11 subjects into the next dose cohort (13.6 mg and/or 54.4 mg C16G2 Varnish or Placebo) or to terminate enrollment based on microbiology data.

After confirmation of study eligibility, subjects will be randomized at Visit 3 (Day 0) by authorized study staff according to the master randomization schedule from the Sponsor's study statistician. The randomization schedule and associated documentation will be kept in a secure location at the study site.

3.1.2 Blinding

The study will be conducted in a single-blind, placebo-controlled manner. All study subjects, parents and legal guardian(s) will be blinded to the treatment assignment, while the Investigator, study staff/clinicians and the Sponsor's assigned team members (e.g., the Clinical Monitor and the Medical Monitor) will be unblinded as to whether subjects are receiving C16G2 or Placebo.

4. SELECTION CRITERIA

4.1 Inclusion Criteria

Subjects are eligible to participate if they meet the following criteria:

1. Males and females, 12-75 years of age
2. Adults subjects provide written informed consent and adolescent subjects give written or verbal assent, as appropriate, and parent(s) or legal guardian(s) give written informed consent
3. Female subjects of childbearing potential must agree to use one of the following forms of contraception from screening through the last study visit: hormonal (oral, implant, or injection) begun >30 days prior to screening; barrier (condom, diaphragm, or cervical cap with spermicide); intrauterine device (IUD). Acceptable contraceptive options may also include abstinence, relationship with a same sex partner or partner who has had a vasectomy at least six (6) months prior to the screening visit
4. Negative urine pregnancy test in all females of childbearing potential (past menarche)
5. Male subjects of sexual activity age: willing to use contraception or abstain from sexual activity beginning with the first exposure to study drug and continuing until discharged from the study due to completion or Early Termination
6. Healthy, as determined by the Investigator (in consultation with the Medical Monitor, as needed), based on medical and dental history, concurrent illnesses, laboratory results, concomitant medications, oral cavity assessment, and targeted physical examination (general, extraoral, head and neck) during Screening.

Note: Subjects on a stable dose of medication may be eligible for screening and will be assessed by the medical monitor on a case-by-case basis.

7. Have a minimum of 12 bicuspids and molars with a minimum of 8 molars and bicuspids NOT having restorations, crowns or sealants
8. Demonstrated ability to expectorate ≥ 2 mL of stimulated saliva in 5 minutes
9. Have a salivary *S. mutans* of 1.0×10^5 CFUs/mL or greater at Screening using MSB agar plating
10. Willing to refrain from using non-study dentifrice and other non-study oral care products (oral care rinses, fluoride products, etc.) during the study
11. Willing to postpone elective dental procedures (e.g., dental cleanings) between Screening and final post-treatment visit (End of Study or Early Termination)
12. Willing and able to comply with oral hygiene and diet instructions
13. Able to communicate with the Investigator/study center personnel, understand and comply with the study requirements, and willing to return for protocol-specified visits at the appointed times

